8.2.4 AE Outcomes

The following terms and definitions are used in assessing the final outcome of an AE:

- Recovered/Resolved - The patient has fully recovered, or by medical or surgical treatment, the condition has returned to the level observed at the first trial-related activity.
- Recovering/Resolving - The condition is improving and the patient is expected to recover from the event.
- Recovered/Resolved with sequelae - The patient has recovered from the condition, but with lasting effect due to a disease, injury, treatment or procedure. If a sequela meets an SAE criterion, the AE must be reported as an SAE.
- Not recovered/Not resolved - The condition of the patient has not improved and the symptoms are unchanged, or the outcome is not known at the time of reporting.
- Fatal - This term is only applicable if the patient died from a condition related to the reported AE. Outcomes of other reported AEs in a patient before he/she died

should be assessed as “recovered”, “recovering”, “recovered with sequelae” or “not recovered”. An AE with fatal outcome must be reported as an SAE.

8.2.5 Laboratory Test and other Test Abnormalities as Adverse Events

A laboratory or other test (ECG, vital signs) abnormality should be reported as an AE if the Investigator considers the abnormality an AE or if the abnormality is associated with accompanying symptoms, requires medical/surgical intervention, leads to a change in study treatment, or results in discontinuation from the trial. When possible, syndromes not laboratory values, should be reported as AEs. For example, elevated hepatic transaminases associated with hepatitis should be reported as “hepatitis” and decreased hemoglobin and hematocrit requiring iron supplementation should be recorded as “anemia.”

8.2.6 Serious Adverse Events

The Investigator is required to determine if each AE is a Serious Adverse Event (SAE). An SAE is any AE occurring after the first dose of study medication and results in any of the following outcomes:

- Death, or
- Is life-threatening, or
- Prolongation of existing hospitalization, or
- Results in a persistent or significant incapacity or substantial disruption of the ability to conduct normal life functions, or
- Is a congenital anomaly/birth defect.

Important medical events that may not result in death, be life threatening, or require hospitalization may be considered SAEs when, based upon appropriate medical judgment, they may jeopardize the patient and may require medical or surgical intervention to prevent one of the outcomes listed in this definition.

In the event of death, the cause of death should be recorded as the SAE (death is an outcome, not the AE itself).

Any planned procedures that require admission to hospital as well as any planned elective procedures (e.g., angioplasty) are not considered SAEs (unless the underlying condition has worsened or the procedure results in a worsening of the patient’s condition). In addition, pregnancy that occurs during the course of the study or absence of a treatment effect will also not be considered to be an SAE and will be collected on a separate CRF.

8.2.7 Reporting for SAEs (24 Hours)

Regardless of causality, an SAE must be followed clinically until resolution or stabilization.

All SAEs after the first dose of study medication must be reported to the Sponsor or the Sponsor’s representative within 24 hours of the investigational site’s knowledge of the

occurrence. The investigational site will either telephone the report to the Sponsor's Medical Monitor (contact information found on the Protocol Title Page) or transmit by email a Serious Adverse Event Report (SAER) to the Sponsor's Medical Monitor or the Sponsor's representative. If the initial report is made via telephone, a completed SAER must be emailed within 24 hours of the site's knowledge of the event. Investigational sites will be provided with SAER forms.

The SAE information phoned or emailed to the Sponsor or the Sponsor's representative will include the following (as available):

- Patient Number, Investigator name, and Site Number
- SAE information: event term, onset date, severity, and causal relationship
- Basic demographic information (e.g., age, gender, weight)
- The outcomes attributable to the event (death, a life-threatening adverse drug experience, inpatient hospitalization or prolongation of existing hospitalization, a persistent or significant disability/incapacity, other important medical event[s])
- A summary of relevant test results, pertinent laboratory data, and any other relevant medical history
- The first and last dates of study medication administration
- A statement whether study medication was discontinued or study medication administration schedule modified
- A statement whether event recurred after reintroduction of study medication if administration had been discontinued or withheld
- Supplemental anonymized information may include the following hospital records: laboratory results, radiology reports, progress notes, admission and emergency room notes, holding/observation notes, discharge summaries, autopsy reports, and death certificates

The SAER should be emailed within 24 hours with as much of the above information as available at the time. Supplemental information may be transmitted using a follow-up report and should not delay the initial report.

For regulatory purposes, initial reports of SAEs should be transmitted within the prescribed time frame as long as the following minimum information is available: patient number, suspect study medication, reporting source, and an event or outcome that can be identified as being both serious and unexpected for which the Investigator can make a relationship assessment.

8.3 Reporting of Pregnancy

Any pregnancy where the estimated date of conception occurs either prior to the End of Study must be reported.

If an adverse outcome of a pregnancy is suspected to be related to study medication exposure, this should be reported regardless of the length of time that has passed since the exposure to study treatment.

An induced abortion or a spontaneous abortion is considered to be an SAE and should be reported in the same timeframe and in the same format as all other SAEs.

Pregnancies must be reported as soon as possible but no later than one business day by fax or email.

All pregnancies must be followed to outcome. The outcome of the pregnancy must be reported as soon as possible but not later than 24 hours of the investigational site's knowledge of the outcome.

9. PHARMACOKINETIC ASSESSMENTS

Not applicable.

10. SCHEDULE OF ASSESSMENTS AND PROCEDURES

The assessments and procedures for this study are described in detail below and presented in the Schedule of Assessments and Procedures located behind the Synopsis.

10.1 Part I

10.1.1 Screening

Potential study patients will be recruited by the study staff from patients who will undergo cardiac surgery with CPB. Prior to performing any study procedures or assessments, the nature of the study and the potential risks associated with the trial will be explained to the potential study patient and written informed consent obtained. Once informed consent has been obtained, the potential study patient will undergo the following study-related procedures and evaluations:

- Review inclusion and exclusion criteria
- Obtain medical history (including history of any medications within 30 days prior to Screening) and demographics (including date of birth, gender, race, and ethnicity)
- Obtain vital signs (SBP, DBP, HR, respiration rate, and body temperature), height, and weight
- Perform comprehensive physical examination
- Perform 12-lead ECG
- Spirometry – only for those patients with presence or history of significant restrictive or obstructive lung disease
- Collect blood for clinical laboratory tests, including serum pregnancy test for women of childbearing potential.

If the patient satisfies all the eligibility criteria, the patient may be enrolled into the study. If the patient is not eligible for the study, the patient will be considered a screen failure.

Note: Before patients may be switched over to VentaProst, patients must meet Inclusion Criteria 4c, that is, demonstrate a clinically defined response to aerosolized Veletri, defined as at least a 15% improvement in one or more hemodynamic parameters (as defined by the clinical team).

10.1.2 Intra-Operative (OR)

The patient will undergo cardiac surgery with CPB in the OR and the following study-related procedures and evaluations:

- Measure hemodynamic parameters prior to cardiac surgery with CPB. These measurements will represent the baseline for hemodynamic parameters.
- Record all cardiovascular procedures and concomitant medications
- Investigator assessment of any unanticipated medical events

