6.2 Treatments Administered

6.2.1 Part I

Post-cardiac surgical patients will initially receive treatment with aerosolized Veletri 50 ng/kg/min in either the OR or the ICU in accordance with each site's standard of care guidelines on administration of aerosolized Veletri. In the ICU, patients who demonstrate at least a 15% improvement in one or more hemodynamic parameters with aerosolized Veletri will be crossed over to a calculated VentaProst equivalent dose of 17 ng/kg/min. The VentaProst dose will then be increased in 20% increments (refer to VentaProst Pharmacy Manual) every 15 minutes to match the clinically meaningful PD measures achieved (i.e., not less than 90% of the effect observed) with the aerosolized Veletri dose.

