10.2.2 Intra-Operative (OR)

The patient will undergo cardiac surgery with CPB in the OR and the following study-related procedures and evaluations:

- Measure hemodynamic parameters prior to cardiac surgery (after induction) with CPB. These measurements will represent the baseline for hemodynamic parameters
- Record all cardiovascular procedures and concomitant medications
- Investigator assessment of any unanticipated medical events

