12. STATISTICAL CONSIDERATIONS

12.1 Statistical Methods

A Statistical Analysis Plan will be developed that describes in detail the statistical methods to be used for analysis of this study and will be finalized prior to database lock.

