12.3 Analyses Sets

All patients who are enrolled in the study and who receive at least one dose of VentaProst will be included in the intent-to-treat (ITT) analyses of pharmacodynamic and safety data. All available data will be used and missing data will not be estimated or carried forward in any statistical summary or analyses.

Descriptive summary statistics include the number of patients, mean, median, percent coefficient of variation (% CV) (if required), standard deviation, and minimum and maximum values (quantitative variables) or the number of patients and percentages by category (qualitative variables). Changes will be assessed as the difference between baseline measurements and the appropriate post-dose measurements unless otherwise specified. Individual patient listings of data will also be provided to allow for review of all pharmacodynamic, safety, and tolerability parameters.

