12.4 Demographic and Other Baseline Characteristics

Continuous demographic and other baseline characteristics (such as age, weight, and height) will be summarized using n, mean, SD, median, minimum, and maximum. Qualitative characteristics (such as gender and race) will be summarized by counts and percentages. Baseline hemodynamic parameters will be obtained prior to cardiac surgery with CPB.

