12.5 Pharmacodynamic Analyses

12.5.1 Primary Endpoint

The primary efficacy endpoint of this study is to determine the equivalent dose of VentaProst necessary to achieve a hemodynamic parameter measurement that is not less than 90% of the effect observed with 50 ng/kg/min aerosolized Veletri.

Further details will be included in the Statistical Analysis Plan.

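### The haemodynamic baseline is the pre-surgery value, so default change scores combine the surgery and bypass shift with the drug effect, and the reference for the 15% and 90% criteria is not stated consistently

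*Combined protocol and SAP*

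**What the plan says.** All references are to the combined protocol; the text available for review contains no separate SAP.

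- **Baseline.** In Part I (Section 10.1.2) haemodynamics are measured "prior to cardiac surgery with CPB. These measurements will represent the baseline for hemodynamic parameters". In Part II (Section 10.2.2) they are measured "prior to cardiac surgery (after induction) with CPB. These measurements will represent the baseline for hemodynamic parameters". Section 12.4 repeats the definition: "Baseline hemodynamic parameters will be obtained prior to cardiac surgery with CPB".
- **Change scores.** Section 12.3: "Changes will be assessed as the difference between baseline measurements and the appropriate post-dose measurements unless otherwise specified".
- **Timing of drug.** Section 6.2.1: "Post-cardiac surgical patients will initially receive treatment with aerosolized Veletri 50 ng/kg/min". Section 6.2.2 also calls the Part II patients post-surgical.
- **Pre-dose values.** These are scheduled in Part I (Table 1 footnote 5, Section 10.1.3) and Part II (Table 2 footnote 5, Section 4.2), but are nowhere named as baseline.
- **15% response.** In Part I the synopsis and Sections 4.1 and 10.1.3 measure before and after Veletri. Table 1 footnote 8 instead judges response from baseline, for inclusion, continuation and transition to VentaProst. In Part II no reference is given.
- **90% match.** Section 12.5.1 asks for "a hemodynamic parameter measurement that is not less than 90% of the effect observed with 50 ng/kg/min aerosolized Veletri". Table 1 footnote 9 speaks of matching the measurements obtained on Veletri. Neither says from what point the effect is measured.
- **Deferral.** Section 12.5.1: "Further details will be included in the Statistical Analysis Plan". Section 12.1 says the SAP "will be finalized prior to database lock".

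**The concern.** A change score meant to describe a drug should start from the patient's state just before the drug. Here the only defined starting point lies before the operation. Anything that anaesthesia, surgery and bypass do to pulmonary pressure, resistance or cardiac output between that point and the first dose is credited to, or subtracted from, the drug.

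Two things are at stake, and they differ in how far they can be repaired. Summary change scores can be recalculated later because pre-dose values are collected. Bedside decisions cannot. In Part I a patient who does not reach 15% on Veletri is withdrawn as a screen failure (Section 10.1.3), so the reference determines who is studied. In Part II it can affect when titration stops. If sites read the passages differently, they will apply different rules to similar patients, with only about 10 patients in each part.

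**Working it through.** The plan gives no figure to reproduce. The documents contain no surgical shift, drug effect or SD, so every such value below is an assumption. Percentages are used because the 15% rule is a percentage; Section 12.3 does not say whether its difference is absolute or relative.

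**1. Effect on a change score.** Set the pre-surgery value to 1, the pre-dose value to 1 + s, and the on-drug value to (1 + s)(1 − d), where s is the shift and d the true fall. The fall from the plan's baseline is 1 − (1 + s)(1 − d). With d = 0.20:

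| Shift s | Calculation | Recorded fall |
|---|---|---|
| −20% | 1 − 0.80 × 0.80 | 36% |
| −10% | 1 − 0.90 × 0.80 | 28% |
| 0 | 1 − 1.00 × 0.80 | 20% |
| +10% | 1 − 1.10 × 0.80 | 12% |
| +20% | 1 − 1.20 × 0.80 | 4% |

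**2. Effect on the 15% call for one parameter.** The recorded fall equals 15% when s = 0.85/(1 − d) − 1. For d = 0.20 this is 0.85/0.80 − 1 = +6.25%; above that shift a true responder is called a non-responder. For d = 0.10 it is 0.85/0.90 − 1 = −5.6%; at that shift or lower a true non-responder is called a responder.

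In assumed mPAP values (pre-surgery, pre-dose, on Veletri, mm Hg):
- 35, 30, 27: 8/35 = 22.9% from pre-surgery, 3/30 = 10.0% from pre-dose.
- 35, 40, 33: 2/35 = 5.7% from pre-surgery, 7/40 = 17.5% from pre-dose.

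**3. Where the reference matters in Part II.** Sections 6.2.2, 6.3.3.2 and 6.3.4.2 titrate until 15% is reached, so there the reference bears directly on stopping. Sections 4.2 and 10.2.3.1 have three branches:
- more than 15% at the initial dose and nothing added by the first escalation: return to the initial dose;
- more than 15% and a further meaningful change: continue escalating;
- less than 15%: continue escalating.

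The last two prescribe the same action. In these sections the reference alters the action only when the first escalation adds nothing. The plateau rule and the return to the best dose compare successive doses and do not depend on it.

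**4. Effect on the 90% match.** Assume 30 pre-surgery, 27 pre-dose and 21.6 on Veletri (mm Hg). The target is:
- pre-surgery reference: 30 − 0.9 × 8.4 = 22.4;
- pre-Veletri reference: 27 − 0.9 × 5.4 = 22.1;
- level match: 21.6.

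The targets differ by 0.8 mm Hg at most. What that means for the titrated dose cannot be calculated from the documents.

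**5. Effect on spread.** Assume a true fall with mean 20% and SD 8 points, and a shift with mean 0 and SD 10%. If the two are independent, the variance is (1 + 0.10²)(0.80² + 0.08²) − 0.80² = 0.01286, an SD of 11.3 points against 8.0 with no shift. If patients with a larger surgical rise also have a larger fall on drug (correlation ρ), the first-order variance is 0.08² + 0.80² × 0.10² − 2 × 0.80 × ρ × 0.08 × 0.10 = 0.0128 − 0.0128ρ. The SD is then about 8.0 at ρ = 0.5 and 5.1 at ρ = 0.8. The spread can rise, stay the same or fall.

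**6. What a pre-Veletri reference leaves in Part I.** If the underlying level falls by r while the patient is on Veletri, a VentaProst effect equal to a 20% Veletri effect reads as 1 − (1 − r) × 0.80. This is 21.6%, 24% and 28% for r = 2%, 5% and 10%.

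**The case against.** The strongest reply is that nothing is final. Section 12.3 allows another reference to be specified, Section 12.5.1 defers to the SAP, and the study is small and described with summary statistics. For change scores this carries weight, since a SAP written before database lock could put them right. It does not remove the defect, because the only haemodynamic baseline the text specifies is the pre-surgery one, and a SAP finalised at that stage cannot revise bedside decisions already made.

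It is also fair that most of the Part I wording points to a pre-Veletri comparison, with footnote 8 standing against it. Actual conduct may follow the majority wording. But footnote 8 is the place that ties the determination to inclusion and transition, so the conflict should not be left.

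Several stronger readings are tempting, and the documents do not support them:
- **That Part II cannot separate surgery from drug.** It can, because each patient has a pre-dose value; the default simply does not use it.
- **That every Part II on-drug value follows completed surgery.** Section 6.2.2 says so, but Section 4.2 lets patients continue VentaProst into the ICU, and dosing may start in the OR. The baseline precedes surgery either way.
- **That all Part II titration depends on the reference.** Step 3 shows that much of it does not.
- **That the change-score SD is necessarily inflated.** Step 5 shows that this needs independence.
- **That a known share of patients will be misclassified.** The criterion is one or more parameters chosen by the clinical team, so single-parameter reversals do not give a trial-level rate.

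**Conclusion.** The concern holds in a limited form. Under the stated default, haemodynamic change scores combine the surgery and bypass shift with the drug effect, and no passage in the supplied text names another analysis reference. The Part I 15% response has two conflicting references. The Part II 15% rule has none, which matters where 15% is the stopping point and, under Sections 4.2 and 10.2.3.1, only when the first escalation adds nothing. The 90% match has no stated reference.

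The size depends wholly on the assumed shift: a true 20% fall can read as anything from 36% to 4% over shifts of −20% to +20%, and the one-parameter 15% call reverses above +6.3%.

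A reader might infer that the primary endpoint, the equivalent dose, is therefore wrong. That is not shown. The 90% target moves little in the mm Hg example, and no effect on the recorded dose can be quantified. Laboratory and ECG baselines, which are set at Screening, are unaffected.

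This should be fixed, and the bedside passages should be reconciled before enrolment.

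**What to change.** **Analysis.** In Sections 12.3 and 12.4 and the baseline sentences of Sections 10.1.2 and 10.2.2, make the last scheduled measurement before the first dose of Veletri (Part I) or VentaProst (Part II) the reference for haemodynamic change scores. Keep the pre-surgery value as a descriptive characteristic. In Part I, also report VentaProst against the last on-Veletri measurement before the switch, which Table 1 footnote 10 already provides for. State openly that recovery over time on Veletri remains in the VentaProst change from the pre-Veletri value. It also remains in the 15% call, because Veletri may start in the OR while response is judged after stabilisation in the ICU.

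**Bedside decisions.** The sponsor must reconcile the following, so that one stated reference applies to the 15% response and the 90% match:
- Part I: Table 1 footnotes 5, 8 and 9 with Sections 4.1, 10.1.2, 10.1.3 and 10.1.4.1;
- Part II: Table 2 footnote 5 with Sections 4.2, 6.2.2, 6.3.3.2, 6.3.4.2, 10.2.2 and 10.2.3.1.

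Section 12.5.1 and the SAP should then give that same reference and the formula for the 90% effect. An analysis reference for the 90% match that differed from the bedside one could not change doses already titrated.

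**Cost.** No new measurements. It does need a protocol amendment, which may require IRB approval under Section 13.2.1.

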10.1.3 Aerosolized Veletri Treatment (OR/ICU)

If there is a need for administration of aerosolized Veletri, the patient will begin dosing at 50 ng/kg/min (in accordance with each site's standard of care guidelines) and will undergo the following study-related procedures and evaluations:

- Measure hemodynamic, oxygenation, and ventilator parameters before aerosolized Veletri administration and after stabilization of aerosolized Veletri
- If at least a 15% improvement in one or more hemodynamic parameters (as defined by the clinical team) is seen with aerosolized Veletri after stabilization in the ICU, the VentaProst will be set-up inline to the ventilator circuit, VentaProst nebulization will be started, and then the Veletri pump flow will be stopped once VentaProst administration is confirmed. Do not remove Veletri administration system until VentaProst administration is confirmed
- If less than a 15% improvement is seen in one or more hemodynamic parameters (as defined by the clinical team) with aerosolized Veletri after stabilization in the ICU, the patient will not be administered VentaProst
- Record all concomitant medications
- Investigator assessment of any unanticipated medical events

If the patient does not require aerosolized Veletri, or if the patient fails to achieve at least a 15% improvement in one or more hemodynamic parameters with aerosolized Veletri, the patient will be withdrawn from the study as a screen failure.

10.1.4 VentaProst Treatment (ICU)

10.1.4.1 Dosing

Patients who demonstrate at least a 15% improvement in one or more hemodynamic parameters with aerosolized Veletri will be eligible to receive VentaProst. Patients will undergo the following study-related procedures and evaluations:

- Patients will be switched from aerosolized Veletri to receive a calculated equivalent starting dose of 17 ng/kg/min VentaProst while still on mechanical ventilation
- Patients will receive increases in the VentaProst dose in 20% increments (refer to VentaProst Pharmacy Manual) every 15 minutes until at least 90% of the hemodynamic effect observed with 50 ng/kg/min aerosolized Veletri is achieved. Once this has been achieved, the patient will remain on a stable dose of VentaProst for at least 15 minutes
- Measure hemodynamic, oxygenation, and ventilator parameters before and after each VentaProst dose
- Record all concomitant medications
- Record AEs

